8.6 Definition of End of Trial

The end of trial is the date of the last visit of the last participant.

8.7 Discontinuation/Withdrawal of Participants from Study Treatment

As detailed in section 8.3, if the participant is found to have inadequate acoustic windows, then they will be unable to participate in the study any further. They will therefore be recorded as a screen failure and withdrawn from the study.

Furthermore, each participant has the right to withdraw from the study at any time and without giving a reason.

In addition, the investigator may discontinue a participant from the study at any time if the investigator considers it necessary for any of the following reason:

- An inability to comply with study procedures

- Significant protocol deviation
- Consent withdrawn

All of the above will be recorded in the case report form (CRF).

8.8 Source Data

Source documents are original documents, data, and records from which participants' CRF data are obtained. These include, but are not limited to, hospital records (from which medical history and previous and concurrent medication may be summarised into the CRF), clinical and office charts, laboratory and pharmacy records, diaries, microfiches, radiographs, and correspondence. Medical records will be used as source documents for the TIA participants.

CRF entries will be considered source data if the CRF is the site of the original recording (e.g. there is no other written or electronic record of data). The CRF will therefore be considered the source document for the healthy control participants.

All documents will be stored within a locked filing cabinet, within a locked office in an access restricted University of Leicester site. On all study-specific documents, other than the signed consent, the participant will be referred by the study participant number/code, not by name.

9. TREATMENT OF TRIAL PARTICIPANTS

9.1 Storage of Study Equipment of Related Apparatus

All study specific equipment is stored securely in the CHIASM laboratory and maintained annually by the Medical Physics department at University Hospitals of Leicester NHS Trust.

9.2 Clinical Care

Throughout the study, TIA patients will continue to receive standard clinical care, which includes (but is not limited to): specialist multi-disciplinary assessment, further radiological investigations, and appropriate investigation and secondary prevention interventions (including antithrombotic/ anticoagulant, BP-lowering and cholesterol-lowering therapies).

10. SAFETY REPORTING

10.1 Definitions

Adverse Event (AE)

An AE or adverse experience is:

Any untoward medical occurrence in a patient or clinical investigation participant, which does not necessarily have to have a causal relationship with his/her treatment.

An AE can therefore be any unfavourable and unintended sign (including an abnormal laboratory finding), symptom or disease temporally associated with the study, whether or not considered related to the study.

Adverse Reaction (AR)

All untoward and unintended responses related to the study.

All cases judged by either the reporting medically qualified professional or the sponsor as having a reasonable suspected causal relationship to the study qualify as adverse reactions.

Severe Adverse Events (SAE)

To ensure no confusion or misunderstanding of the difference between the terms “serious” and “severe”, which are not synonymous, the following note of clarification is provided:

The term “severe” is often used to describe the intensity (severity) of a specific event (as in mild, moderate, or severe myocardial infarction); the event itself, however, may be of relatively minor medical significance (such as severe headache). This is not the same as “serious”, which is based on patient/event outcome or action criteria usually associated with events that pose a threat to a participant’s life or functioning. Seriousness (not severity) serves as a guide for defining regulatory reporting obligations.

Serious Adverse Event or Serious Adverse Reaction (SAR)

A serious adverse event or reaction is any untoward medical occurrence that:

- Results in death
- Is life-threatening

NOTE: The term "life-threatening" in the definition of "serious" refers to an event in which the participant was at risk of death at the time of the event; it does not refer to an event which hypothetically might have caused death if it were more severe.

- Requires inpatient hospitalisation or prolongation of existing hospitalisation
- Results in persistent or significant disability/incapacity, or
- Is a congenital anomaly/birth defect
- Other important medical events*

*Other events that may not result in death, are not life threatening, or do not require hospitalisation, may be considered a serious adverse event when, based upon appropriate medical judgement, the event may jeopardise the patient and may require medical or surgical intervention to prevent one of the outcomes listed above.

Expected Serious Adverse Events/Reactions

See Appendix D for a complete list of expected adverse events not subject to immediate reporting.

Suspected Unexpected Serious Adverse Reactions (SUSAR)

A serious adverse reaction, the nature or severity of which is not consistent with the applicable product information.

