6.2 Primary and Secondary Endpoints/Outcome Measures

This is not an intervention study, and therefore it would not be appropriate to assess classical primary and secondary outcome measures such as death and disability for this study. However, we intend to evaluate the following relevant outcomes:

- a) The number of participants recruited
- b) The number of participants able to comply with the full measurement protocol
- c) The number of measurements rejected because of aspects related to data quality during the analysis protocol, with recorded reasons
- d) Overall, the number of recruited subjects in whom values for the following parameters can be derived:
 - % change of cerebral blood flow velocity (CBFv) at baseline in response to performance of a squat-stand manoeuvre
 - Autoregulation index

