- 3) A recording during which the participant is asked to stand for 10 seconds before squatting down and remaining in a squat position for 10 seconds before standing back up and then repeating this process for 5 minutes. A computer program will provide visual cues to the participant to guide the timings of the squat-stand sequence. As each squat manoeuvre (consisting of a squat down and stand back up) will last for 20 seconds, the participant will be required to perform a total of 15 squats in the 5 minute period. This recording will begin and end with a period of 90 seconds baseline recording where the participant stands quietly with their eyes open.

A period of instruction will precede recording 3 during which the SSM will be demonstrated. During squats, participants will be asked to breathe through their nose and to avoid straining if possible. Participants will be instructed to squat down as low as they feel able. They will be informed that they will need to perform a maximum 15 squats and to take this into account when choosing their depth. Participants will be informed that they should try to complete all 15 squats if possible. However, if they wish to stop the SSM before this, they should make the investigator aware during a standing period and ideally remaining standing for a further 90 seconds before being disconnected from the equipment.

During the recordings the internal plethysmography servo-adjust of the Finometer will be switched off, but this will be switched back on in between each recording to allow for accurate calibration of BP. A brachial BP will also be taken in between each recording using the same validated UA767 BP monitor as at the beginning of the baseline assessment.

Participants will be allowed to rest for as long as needed before leaving the laboratory at the end of the study measurement. Refreshments will be provided, and travel expenses will be refunded.

There is a very small chance that the 3 lead ECG could detect a heart abnormality (arrhythmia) in either the healthy controls or the patient participants. Should this situation occur, we would explain our findings to the participant and notify their GP. Formal written consent will be obtained to cover this circumstance.

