10.3 Reporting Procedures for Serious Adverse Events

All SAEs, except those expected ones defined in Appendix D that do not require immediate reporting (see Appendix D), must be reported to the Sponsor within 24 hours of discovery or notification of the event. The Sponsor will perform an initial check of the information and ensure that it is reviewed at the next R&D Management meeting. All SAE information must be recorded on an SAE form and sent to the Sponsor using the appropriate reporting form and the contact details on there. Additional information received for a case (follow-up or corrections to the original case) needs to be detailed on a new SAE form which must be sent to the Sponsor using the appropriate reporting form and the contact details on there.

The Sponsor will report all SUSARs to the Research Ethics Committee concerned. Fatal or life-threatening SUSARs must be reported within 7 days and all other SUSARs within 15 days. The CI will inform all investigators concerned of relevant information about SUSARs that could adversely affect the safety of participants.

In addition to the expedited reporting above, the CI shall submit once a year throughout the study or on request an Annual Report to the Ethics Committee which lists all SAEs / SUSARs that have occurred during the preceding 12 months.

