16. STUDY GOVERNANCE

The trial management group, which consists of the CI, co-investigators, and other research staff, will meet monthly to monitor study progress, and recruitment targets. As this is a prospective case control study, and not a therapeutic study, a data safety monitoring committee is not required.

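### For events listed in Appendix D that the squat-stand test causes, the protocol's two references for 'unexpected' disagree on whether the 7- or 15-day ethics committee report is due

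*Combined protocol and SAP*

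**What the plan says.** Section 10.1 defines an adverse reaction by its relation to the study as a whole: "All untoward and unintended responses related to the study". It then defines a SUSAR as "A serious adverse reaction, the nature or severity of which is not consistent with the applicable product information".

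Section 10.3 attaches the reporting duty to that label. "The Sponsor will report all SUSARs to the Research Ethics Committee concerned", and "Fatal or life-threatening SUSARs must be reported within 7 days and all other SUSARs within 15 days".

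Directly above the SUSAR definition, under a heading that covers expected serious events and reactions together, section 10.1 gives a second reference: "See Appendix D for a complete list of expected adverse events not subject to immediate reporting". Section 10.3 uses that list to exempt listed serious events from the 24-hour report to the Sponsor.

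No product is described. Section 6.2 states "This is not an intervention study". The main physical exposure is the manoeuvre in section 8.5, in which "the participant will be required to perform a total of 15 squats in the 5 minute period", although participants may stop early. On oversight, section 16 says "As this is a prospective case control study, and not a therapeutic study, a data safety monitoring committee is not required".

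**The concern.** Whether a serious reaction is unexpected decides whether the ethics committee hears of it within days. The definition refers the assessor to a document that this study does not have. The list beside it was not written for the purpose: it does not separate complications of vascular disease and ageing from what repeated squatting might cause.

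The consequence concerns participant safety, not the analysis. The test induces large blood pressure changes (section 4) in people within 7 days of a TIA. The populations that section 4 names as having tolerated it are heart transplant recipients, healthy controls and patients with Alzheimer's dementia. There is no data safety monitoring committee, and the management group consists of the study's own staff. Apart from the SUSAR report, section 10.3 gives the committee an annual report, or one on request. The planned trial period is six months, so a first annual report could arrive after every participant has been tested.

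**Working it through.** No arithmetic applies. The check sets the provisions side by side and runs cases through them.

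**Inputs**

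- Test for a reaction: related to the study (10.1).
- Test for unexpected in the SUSAR definition: product information (10.1). No brochure, device manual or other reference document is named. The nearest wording is a field for a suspect device in the adverse event record (10.2).
- Second source on expectedness: Appendix D, presented in 10.1 as complete. Its title excludes the listed events from expedited reporting.
- Consequence of the SUSAR label: a committee report in 7 or 15 days, made by the Sponsor (10.3).
- Consequence of an Appendix D listing: no 24-hour report to the Sponsor (10.3).

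**Cases: a serious event judged related to the squat-stand test**

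| Event | SUSAR definition | Appendix D | Do they agree? |
|---|---|---|---|
| Listed: syncope, fall, fracture, stroke, myocardial infarction | No product information to be consistent with: unexpected by default, or not assessable | Expected | No |
| Not listed: for example, admission for arrhythmia, or joint injury | As above | Not on the complete list, so unexpected | Yes on the default reading; no contradiction on the other |

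**Listed events.** Under the default reading of the definition, the 7- or 15-day report is due. Under Appendix D it is not, and the committee's scheduled notice is the annual report.

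**Unlisted events.** Appendix D and the default reading both start the clock, and the Sponsor is told within 24 hours. What is missing is only a correctly named reference.

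**Can Appendix D stand in for product information?** Not as written. The SUSAR definition does not point to it. It does not say whether its events are expected from disease or from the manoeuvre. It also gives no severities, although the definition tests both nature and severity.

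**Would correcting the definition be enough?** No. The Sponsor makes the committee report, and 10.1 gives the Sponsor a part in judging causality. Yet 10.3 exempts every Appendix D event from 24-hour notice, without regard to relatedness. A squat-related syncope could then be a SUSAR by definition while no stated deadline brings it to the Sponsor. The definition and the exemption have to change together.

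**The case against.** The best defence is that section 10.1 does supply a workable reference. Its heading covers reactions as well as events and leads straight to Appendix D, whose title rules out expedited reporting. On that view Appendix D governs, and the phrase about product information is left over from a product-trial template. That reading is natural, but it does not remove the problem. The template phrase is still the stated trigger. If Appendix D does govern, a stroke or syncope caused by the test is reported quickly neither to the Sponsor nor to the committee.

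Other points stand as context. All adverse events go on the CRF, and a medically qualified investigator assesses relatedness (10.2), so such an event would not go unrecorded. Sponsor SOPs apply (14.2). They are not visible, so practice may be better than the text, but they do not cure it. The measuring equipment may have manufacturer information, but the protocol does not name it as the reference, and a reaction to squatting is not a reaction to that equipment.

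A reader might infer that no serious reaction to the test can be classified, and so that every one is affected. The documents do not support this. An unlisted reaction is unexpected by Appendix D and by the default reading of the definition, and it reaches the Sponsor in 24 hours. An assessor could insist on the literal reading that nothing can be assessed without product information, but that is a gap in the reference and not a conflict between two references.

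**Conclusion.** The text is wrong as written and should be corrected. The conflict is confined to serious events that are on Appendix D and judged related to a study procedure. For these, the committee report is due in 7 or 15 days on one reading and left to the annual report on the other, in a study planned to last six months. For unlisted reactions the defect is one of naming.

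The documents give no rate of serious events during squat-stand testing, so the number affected cannot be estimated. With 40 participants (20 TIA, 20 controls) attending once, few are likely. No objective, endpoint or analysis is affected.

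The conclusion assumes that no product information outside these documents has been designated as the reference, and that an assessor without one treats a reaction as unexpected by default. If the assessor instead calls it not assessable, the listed events still have no consistent answer.

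**What to change.** Reconcile section 10.1, section 10.3 and Appendix D in one amendment:

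1. In 10.1, replace the reference to product information with one named, procedure-based reference. A SUSAR becomes a serious adverse event judged related to a study procedure (TCD, monitoring or squat-stand manoeuvre) that is not listed in the protocol, in nature and severity, as an expected effect of that procedure.
2. Add the list of expected procedure effects. The sponsor and investigators decide what goes on it.
3. State in 10.1 and Appendix D that the appendix covers events expected from underlying disease, and align the 10.1 heading so that it no longer extends to reactions.
4. In 10.3, limit the exemption from 24-hour Sponsor reporting to Appendix D events judged unrelated to study procedures, so that a listed event caused by the test reaches the Sponsor in time.

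The 7- and 15-day limits stay unchanged. The cost is a wording amendment through the approvals in section 14.5, and possibly a few more expedited reports in a 40-person, single-visit study.

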10.2 Reporting procedures for All Adverse Events

All AEs occurring during the study observed by the investigator or reported by the participants, whether or not attributed to study, will be recorded on the CRF.

The following information will be recorded: description, date of onset and end date, severity, assessment of relatedness to study, other suspect device and action taken. Follow-up information should be provided as necessary.

AEs considered related to the study as judged by a medically qualified investigator or the sponsor will be followed until resolution or the event is considered stable. All related AEs that result in a participant's withdrawal from the study or are present at the end of the study, should be followed up until a satisfactory resolution occurs.

It will be left to the investigator's clinical judgment whether or not an AE is of sufficient severity to require the participant's removal from the study. A participant may also voluntarily withdraw from the study due to what he or she perceives as an intolerable AE.

The severity of events will be assessed on the following scale: 1 = mild, 2 = moderate, 3 = severe.

The relationship of AEs to the study will be assessed by a medically qualified investigator.

10.3 Reporting Procedures for Serious Adverse Events

All SAEs, except those expected ones defined in Appendix D that do not require immediate reporting (see Appendix D), must be reported to the Sponsor within 24 hours of discovery or notification of the event. The Sponsor will perform an initial check of the information and ensure that it is reviewed at the next R&D Management meeting. All SAE information must be recorded on an SAE form and sent to the Sponsor using the appropriate reporting form and the contact details on there. Additional information received for a case (follow-up or corrections to the original case) needs to be detailed on a new SAE form which must be sent to the Sponsor using the appropriate reporting form and the contact details on there.

The Sponsor will report all SUSARs to the Research Ethics Committee concerned. Fatal or life-threatening SUSARs must be reported within 7 days and all other SUSARs within 15 days. The CI will inform all investigators concerned of relevant information about SUSARs that could adversely affect the safety of participants.

In addition to the expedited reporting above, the CI shall submit once a year throughout the study or on request an Annual Report to the Ethics Committee which lists all SAEs / SUSARs that have occurred during the preceding 12 months.

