6. STUDY DESIGN

6.1 Summary of Trial Design

This is a single-centre, prospective, case control study which will run for six months. 20 patients with acute TIA (within 7 days), and 20 healthy controls will be recruited from the specialist TIA clinic at University Hospitals of Leicester NHS Trust. Participants will be eligible if they are aged over 18 and can consent to participate. They won't be able to participate if they have severe heart failure, an irregular heartbeat, blocked neck blood vessels, severe breathing problems, if they do not understand written or verbal English, if they have inadequate ultrasound windows, or if they are pregnant.

TIA participants will be given a minimum of 1 hour, and a maximum of 48 hours to decide whether or not to take part in the study, but must undertake the study assessment within 7 days of their TIA. Healthy control participants will be given a minimum of 1 hour, and a maximum of 7 days to decide whether or not to take part in the study. There is no time restriction on when they undertake the study assessment.

All participants will undergo an assessment of brain blood flow using TCD, during which their heart rate, breathing and blood pressure will also be monitored. During the assessment participants will sit quietly before being asked to stand and then complete a squat-stand manoeuvre in time with a computer sequence. The research visit will take approximately 90 minutes, the TCD assessment itself will take approximately 1 hour and participants only need to attend once.

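### Section 10.3 lifts the 24-hour report to the sponsor for every serious event listed in Appendix D, even one caused by the squat-stand test, and states no other time limit for it

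*Combined protocol and SAP*

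**What the plan says.** Section 10.3 gives 24 hours, from discovery or notification, for an SAE to reach the sponsor. The rule opens with its exception: "All SAEs, except those expected ones defined in Appendix D that do not require immediate reporting". Section 10.1, under the heading "Expected Serious Adverse Events/Reactions", refers to Appendix D for the complete list of these events. Appendix D is a plain list of terms with no footnote or condition.

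Section 10.3 then adds: "All SAE information must be recorded on an SAE form and sent to the Sponsor". The sponsor makes an initial check and has the information reviewed at its next R&D Management meeting. For suspected unexpected serious adverse reactions (SUSARs), section 10.3 says "The Sponsor will report all SUSARs to the Research Ethics Committee concerned" and "Fatal or life-threatening SUSARs must be reported within 7 days and all other SUSARs within 15 days". Section 10.1 defines a SUSAR by comparing the nature or severity of the reaction with product information.

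Section 10.2 requires every adverse event to be recorded on the CRF, with its onset date and an assessment of relatedness by a medically qualified investigator.

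**The concern.** An exemption for expected events is sensible where the background rate is high. Section 4 says that one in 12 people have a full stroke within a week of a TIA, and such strokes need not trigger an urgent report if the study had no part in them.

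The exemption here is wider than that. It turns only on whether the event is on the list. It does not ask whether the study caused the event, and it applies to healthy controls as well as TIA patients.

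The study procedure is up to 15 squat-stands in 5 minutes (section 8.5), chosen because the manoeuvre produces large blood pressure changes (section 4). My judgement, which the protocol does not state, is that syncope, a fall, a fracture or a vascular event are the harms one would first look for from such a test. All are on the list. So the events most informative about the safety of the test are the ones for which prompt notice to the sponsor is switched off.

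**Working it through.** No figure in the plan needs reproducing. The check is a count of the list, followed by a trace of each reporting route.

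**Size of the list.** Appendix D is laid out as 23 rows of two terms and one row of one term: 23 × 2 + 1 = 47 terms. Stroke, TIA, syncope, fall, fracture and myocardial infarction are all present (6 of 6).

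**Whole list or subset?** The words in section 10.3 could be read as exempting only some Appendix D events. Section 10.1 and the Appendix D heading both treat the whole list as exempt, and no term is marked differently from another.

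**Routes for a listed SAE caused by the squat-stand test.**

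| Route | Source | Applies? | Time limit stated |
|---|---|---|---|
| Report to sponsor | 10.3 | No, exempt | 24 hours, for unlisted SAEs only |
| SAE form to sponsor | 10.3 | Yes | None |
| CRF entry | 10.2 | Yes | None; a recording duty only |
| Sponsor's initial check and R&D Management review | 10.3 | Once the sponsor has the information | Next meeting; no date |
| SUSAR report, sponsor to ethics committee | 10.1, 10.3 | Unclear | 7 or 15 days |
| Sponsor SOPs | 14.2 | Possibly | Not in the documents |

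The like-for-like comparison is the step from site to sponsor: 24 hours for an unlisted SAE, no stated limit for a listed one. The sponsor's review and any SUSAR report come after that step and depend on it.

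**Why the SUSAR row is unclear.** The only definition, in section 10.1, uses product information and does not mention Appendix D. On that wording a serious event caused by squatting may well be unexpected, and so a SUSAR. But Appendix D labels the same events expected and takes them out of expedited reporting, and the section 10.1 heading that leads to it covers reactions as well as events, although the sentence beneath refers only to events. Section 8.5 names several commercial measuring devices, but the protocol does not say which product information is meant or how it would bear on a squatting manoeuvre. The two tests can therefore give opposite answers for one event.

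**Relatedness.** Section 10.2 already collects it for every event. Section 10.3 does not use it to restore the 24-hour duty.

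**The case against.** The strongest reply is that listed SAEs are not lost. They are recorded, sent to the sponsor on a form, checked, reviewed at an R&D Management meeting and listed in the annual report. If the event is a SUSAR, the 7- or 15-day rule covers all of them without exception. Sponsor SOPs may date the form. The study is single-centre, so those running the test would know at once of an event during the visit. All of this stands, and it limits the point to the timing of notice to the sponsor and the classification of the event. It does not close the gap, because the later steps need the sponsor to have been told and the protocol does not say by when.

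Two stronger readings are tempting, and the documents support neither.

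- A reader might set the 24 hours against the annual report, due "once a year throughout the study or on request an Annual Report to the Ethics Committee which lists all SAEs", note that "This is a single-centre, prospective, case control study which will run for six months", and infer a delay of many months caused by the exemption. That report goes from the chief investigator to the ethics committee, so it is a different step. An unlisted SAE that is not a SUSAR has no earlier dated report to that committee either.
- A reader might note that "participants only need to attend once" and count the visits still to come after an early event as exposure caused by the missing deadline. No section says that visits pause after a 24-hour report, so that count does not measure what the deadline would prevent.

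Nor does section 4 show that the test is hazardous after TIA. Acute TIA is not among the populations it names as tolerating squat-stands, but its list is introduced as examples only.

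**Conclusion.** The point holds and should be fixed. All 47 Appendix D terms are exempt from the 24-hour report whatever their cause, and no section restores a limit for a listed SAE that the test brought about. It would be too strong to say that such an event has no deadline at all, since the SUSAR rule may apply and sponsor SOPs may set one. The supportable statement is that the protocol states no time limit from site to sponsor and leaves SUSAR status unsettled.

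Confidence is high for what the protocol says and omits. It is lower for any delay in practice, which depends on SOPs and on a reporting form that cannot be seen here. How many events would be affected cannot be estimated without a rate of test-related events. The consequence is for safety oversight. Section 16 provides no data safety monitoring committee and gives the monthly management group the task of watching progress and recruitment targets, so timely notice to the sponsor carries more weight.

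**What to change.** Amend section 10.3 and Appendix D so that the exemption does not cover any SAE, in either group, that meets the causality test section 10.1 already uses for an adverse reaction. Such an event then goes to the sponsor within the existing 24 hours. Listed events judged unrelated can stay exempt.

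Reconcile section 10.1 with Appendix D: define SUSAR expectedness against the study procedures in place of product information, and state that being listed in Appendix D does not by itself make a related event expected.

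Optionally, extend the 24-hour rule to any SAE that starts during the study visit, so that it does not wait on a causality judgement. The documents contain no criterion that requires this, so it is a matter of preference.

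The cost is a change of wording and possibly a few extra 24-hour forms. No visit or data item is added, because section 10.2 already records onset date and relatedness.
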